#### **10.1.5 Local Skin Reaction Score**

The Investigator (or designee) will use the Local Skin Reaction (LSR) Score (see Section 22.1) to numerically assess the overall degree of erythema, edema, weeping / exudate, vesicles, erosions / ulcerations, scaling / dryness, scabbing / crusting, itching, or pain) in the Treatment Field on a 5-point scale, from 0 (none) to 4 (severe). This assessment will be performed on Day 1 Pre-Dose (baseline) and repeated at each subsequent visit. The individual scores for each potential finding will be recorded in the respective cells by the assessor.

In this trial LSRs will be collected independently of AEs. Details regarding reporting are included in Section 15.1.

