## 15. ADVERSE EVENTS

### 15.1 Adverse Event Definition

An AE is any untoward medical occurrence in a subject administered a pharmaceutical product, which does not necessarily have to have a causal relationship with the pharmaceutical product treatment. Any worsening of the subject's disease under study or other medical conditions will also be considered to be an AE, unless it is within the normal range of disease fluctuation for that subject.

**In this trial LSRs will be collected independently of AEs. Any LSR that occurs within the selected Treatment Field and extends to adjacent surrounding skin (defined as within a 2 cm border around the Treatment Area) will be considered LSRs and will not be recorded as AEs. LSRs that require medical intervention (prescription medication) or extend beyond the 2 cm surrounding skin should be documented as an AE.**

Clinically meaningful (for a given subject) changes in physical examination and test findings should also be recorded as AEs. The criteria for determining whether an abnormal objective test finding should be reported as an AE are as follows:

1. Test result is associated with accompanying symptoms, and/or
2. Test result requires additional diagnostic testing or medical/surgical intervention, and/or
3. Test result leads to a change in study dosing or discontinuation from the study, significant additional concomitant drug treatment, or other therapy, and/or
4. Test result leads to any of the outcomes included in the definition of a SAE.

Merely repeating an abnormal test, in the absence of any of the above conditions, does not meet Condition 2 above for reporting as an AE.

Any abnormal test result that is determined to be an error does not require reporting as an AE.

Treatment Emergent Adverse Events (TEAEs) are AEs that occur *de novo* or worsen following the initiation of study treatment.

Surgical procedures themselves are not AEs; they are therapeutic measures taken for the AE, and should be documented as such.

Planned hospital admissions documented in the subject's CRF prior to randomization and study-related procedures are also not AEs.

Overdoses of the study drug will not be reported as an AE. However, any AEs or SAEs, as defined in Section 15, associated with an overdose will be reported as such.

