## 22. APPENDICES

### 22.1 Local Skin Reaction Score

This score has been modified from a score published in Lebwohl M et al (2012), “Ingenol Mebutate Gel for Actinic Keratosis”, *N Engl J Med* 2012;366:1010-9).

The Local Skin Reaction Score is an assessment of all the skin in the Treatment Field (not of the AK lesions). At each study visit the Investigator (or designee) will assign a severity score to each of the objective and subjective findings listed in the table. For example, if the Treatment Field contains vesicles of moderate severity, the number 3 would be placed under the field labelled “Vesicles”.

[figure not shown]
The Investigator will assess the selected Treatment Field and rate the findings on a 5 point scale. The LSR score will consist of the sum of all the individual severity scores.

Treatment Field Findings	Erythema	Edema	Weeping or Exudate	Vesicles	Erosion or Ulceration	Scaling or Dryness	Scabbing or Crusting	Itching	Pain
Severity Score									

The 5 point LSR Score is: **0 = No reaction, 1=Trace reaction, 2= Mild reaction, 3=Moderate reaction, and 4=Severe reaction.**

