### 5.6.7 Safety analysis

- 5.6.7.1 All safety data will be summarized for the ITT population.
- 5.6.7.2 Adverse events will be coded according to coding dictionaries (MedDRA version 19.1 or higher) and presented in tables by System Organ Class (SOC) and Preferred Term (PT) and by treatment group.
- 5.6.7.3 Secondary analysis
  - 5.6.7.3.1 The within-group changes from baseline to each visit in the Composite Local Skin Reaction score and in all of its components will be analyzed using Paired t-test or Signed- rank test for two means (paired observations, as is appropriate).
  - 5.6.7.3.2 The within-group changes from baseline to each visit in the Composite Local Skin Reaction score and in all of its components will be analyzed using Paired t-test or Signed- rank test for two means (paired observations, as is appropriate) on the Day 84 completers subgroup.
  - 5.6.7.3.3 A figure of the Composite Local Skin Reaction score, of the erythema component, and of the edema component by visit and by treatment group will be generated.
- 5.6.7.4 The incidence of AEs and TEAEs, as well as the intensity and relationship to study drug will be summarized by treatment group.
- 5.6.7.5 Safety will also be assessed by evaluating findings of physical examinations, vital signs, clinical laboratory test results, 12-lead ECG tracings, concomitant medications, and withdrawals/terminations/drug holiday/dosing adjustment by treatment group.
- 5.6.7.6 ECG data will be derived from 12-lead ECG tracings (and from cardiac Holter monitoring recordings, if appropriate).
- 5.6.7.7 Summary statistics for observed measures and changes from pre-dose in the following ECG variables will be tabulated at each post-baseline visit:
  - 5.6.7.7.1 Heart rate (bpm)
  - 5.6.7.7.2 PR interval (ms)
  - 5.6.7.7.3 QRS complex (ms)
  - 5.6.7.7.4 QT interval (ms)

	DOCUMENT NUMBER: 029-BST-PLN-001	PAGE: 34 of 45
TITLE: Statistical Analysis Plan for study: A Phase 2 Randomized, Double-Blind, Placebo-Controlled, Parallel-Cohort Study to Evaluate the Efficacy, Safety, Tolerability, and Pharmacokinetics of Once-Daily Application of Topical VDA-1102 Ointment for 28 Days in Subjects with Actinic Keratosis	EFFECTIVE DATE : 22/MAY/2017 REVISION NUMBER : 2.0	

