TITLE: Statistical Analysis Plan for study:  A Phase 2 Randomized, Double-Blind, Placebo-Controlled, Parallel-Cohort Study to Evaluate the Efficacy, Safety, Tolerability, and Pharmacokinetics of Once-Daily Application of Topical VDA-1102 Ointment for 28 Days in Subjects with Actinic Keratosis	EFFECTIVE DATE : 22/MAY/2017 REVISION NUMBER : 2.0	

Table 14.3.5-5: Frequency of Urinalysis Results

Table 14.3.5-6: Summary Statistics of Urinalysis Results

Table 14.3.5-7: Summary Statistics of Urinalysis Changes from Baseline

Table 14.3.5-8: Summary Statistics of Vital Signs

Table 14.3.5-9: Summary Statistics of Vital Signs Change from Baseline

Table 14.3.5-10: Frequency of Vital Signs Abnormalities

Table 14.3.5-10: Physical Examination

Table 14.3.5-11: Shift Tables from Baseline for Physical Examination

Table 14.3.5-12: ECG

Table 14.3.5-13: Shift Table for ECG

Table 14.3.5-14: Individual Components of Local Skin Reaction Score

Table 14.3.5-15: Local Skin Reaction Score

Figure 14.3.1 Local Skin Reaction Score by Visit and by Study Group

Figure 14.3.2 Erythema Component by Visit and by Study Group

Figure 14.3.3 Edema Component by Visit and by Study Group

Table 14.3.5-16: Change in Individual Components of Local Skin Reaction Score from Baseline

Table 14.3.5-17: Change in Local Skin Reaction Score from Baseline

Table 14.3.5-18: Any Concomitant Medications

MediStat Statistics in Medicine	DOCUMENT NUMBER: 029-BST-PLN-001	PAGE: 44 of 45
TITLE: Statistical Analysis Plan for study:  A Phase 2 Randomized, Double-Blind, Placebo-Controlled, Parallel-Cohort Study to Evaluate the Efficacy, Safety, Tolerability, and Pharmacokinetics of Once-Daily Application of Topical VDA-1102 Ointment for 28 Days in Subjects with Actinic Keratosis	EFFECTIVE DATE : 22/MAY/2017 REVISION NUMBER : 2.0	

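### No worst post-baseline grade, share of subjects ever moderate or severe, or between-arm comparison is specified for local skin reactions, most of which are not recorded as AEs

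*SAP*

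**What the plan says.** Protocol 15.1 separates the two data streams: "In this trial LSRs will be collected independently of AEs". Reactions in the Treatment Field and the surrounding 2 cm "will be considered LSRs and will not be recorded as AEs". There are two exceptions: "LSRs that require medical intervention (prescription medication) or extend beyond the 2 cm surrounding skin should be documented as an AE".

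Protocol 22.1 grades nine findings from 0 to 4, with "3=Moderate reaction, and 4=Severe reaction" at the top of the scale. The composite is their total: "The LSR score will consist of the sum of all the individual severity scores". On timing, Protocol 10.1.5 states: "This assessment will be performed on Day 1 Pre-Dose (baseline) and repeated at each subsequent visit". The schedule of assessments gives six post-baseline visits (Days 7, 14, 28, 35, 56 and 84).

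SAP 5.6.7.3 sets the analysis: "The within-group changes from baseline to each visit in the Composite Local Skin Reaction score and in all of its components will be analyzed", by paired t-test or signed-rank test. The same is repeated in Day 84 completers, and figures by visit and group are planned for the composite, erythema and edema. Appendix I lists "Table 14.3.5-17: Change in Local Skin Reaction Score from Baseline" and its component counterpart (14.3.5-16), together with score tables for the components (14.3.5-14) and the composite (14.3.5-15). Appendix II lists individual scores (16.2.8-13).

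Protocol 17.2.2 includes the LSR score among the safety findings to be compared between treatments as well as with baseline.

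**The concern.** Local skin tolerability is part of a secondary objective (Protocol 6, SAP 5.1.1.2). Protocol 5.3 argues for the drug by contrast with field treatments that cause severe local reactions. The natural question is what share of subjects on each arm had a moderate or severe reaction at any time, and how that compares with placebo. Nothing in the SAP answers it directly.

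The gap matters because a grade 4 reaction that meets neither exception in Protocol 15.1 does not enter the AE severity tables. Such reactions may also be short-lived. Protocol 7.6 allows the drug to be stopped for up to 7 days, so a subject may peak at one visit and score low at the next. If subjects peak at different visits, each visit's mean or percentage captures only some of those affected. The composite adds to this: one finding at grade 4 contributes 4 points to a total that runs to 36.

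**Working it through.** The documents state no LSR rate or target, so there is no LSR figure to reproduce. The rates below are assumptions. The ratio between the two kinds of summary depends only on how the peaks spread over visits.

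**Denominator.** The plan's 84 subjects at 1:1:1 give 84/3 = 28 per arm. This agrees with its own sizing: 75/(1 − 0.10) = 83.3, rounded up to 84. An effect size of 0.83 at two-sided 0.045 and 80% power needs 24.6 per arm by the noncentral t, so 25; power at 25 is 80.7%.

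**Composite range.** 9 findings × 4 = 36, so one grade 4 finding is 4/36 = 11% of the range.

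**Dilution formula.** Suppose a share *p* of an arm is ever at grade 4 in one component, each affected subject is at 4 on *m* of *V* visits and at 0 otherwise, and the peaks are spread evenly. Then:
- per-visit share = *p* × *m*/*V*;
- per-visit mean change = 4 × *p* × *m*/*V*;
- understatement factor = *V*/*m*.

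**Four visits (Days 7, 14, 28, 35), one peak each (*m* = 1, *V* = 4).**

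| Ever severe | Shown per visit | Mean component change per visit |
|---|---|---|
| 10% | 2.5% | 0.1 |
| 20% (5.6 of 28) | 5% (1.4 of 28) | 0.2 |
| 30% | 7.5% | 0.3 |

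If every reaction lasted through all four visits (*m* = 4), the factor would be 1 and nothing would be lost.

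**Whole-number example, 6 of 28 ever severe, one peak each.**
- Ever severe: 6/28 = 21.4%, exact 95% CI 8.3% to 41.0%.
- Peaks spread over three visits: 2/28 = 7.1% per visit, mean change 8/28 = 0.29. The mean of each subject's worst change is 24/28 = 0.86.
- The planned test at one visit (two subjects at +4, 26 at 0) gives t = 1.44 on 27 df, p = 0.16; signed-rank also gives p = 0.16.
- Against placebo with none affected, Fisher's exact test gives p = 0.49 for 2/28 at a single visit and p = 0.023 for 6/28 ever.

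A within-group test on the worst score would give p = 0.011 (t) or 0.014 (signed-rank). That should not be relied on, because the maximum of several readings is biased upward from baseline in every arm. The comparison that counts is with placebo.

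**Can per-visit percentages be added up?** No. Two subjects at grade 4 at each of three visits could be anything from 2 distinct subjects (7.1%) to 6 (21.4%). Per-visit tables cannot tell these apart.

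**The case against.** Several stronger readings are tempting, and the documents do not support them.

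- *A reader might infer that LSRs are kept out of the AE tables altogether.* They are not. A reaction that needs prescription medication or spreads beyond 2 cm is an AE, so some of the clinically important reactions will appear there.
- *A reader might infer that LSR is analysed only as change.* Change is the only quantity tested. Scores are also tabulated, plotted and listed.
- *A reader might infer that severe grades will never be reported.* Only table titles are shown. Under SAP 5.6.1.1, Table 14.3.5-14 would give frequencies per grade if the components are treated as categorical, or a maximum that reveals a grade 4 if treated as continuous.
- *A reader might infer that subjects who react and pause disappear from view.* SAP 5.6.7.5 evaluates drug holidays, dosing adjustments and withdrawals by group, and Protocol 7.5.1 requires the reason for each holiday or adjustment to be documented.

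It is also fair to say that per-visit display is this SAP's convention (its QT threshold counts in 5.6.7.9 are per visit too), that the components are tested separately as well as summed, that comparing treatments could mean side-by-side tables and not a test, and that the nonclinical skin findings were described as mild and reversible (Protocol 5.6.1).

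All of this narrows the point but does not remove it. None of these outputs gives the share of subjects ever at a given grade. Per-visit frequencies cannot be summed to obtain it, a listing leaves the reader to count by hand, and holidays or withdrawals are not a graded measure of skin reaction.

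**Conclusion.** The point holds in a limited form. For LSRs outside the two AE exceptions, the score is the main graded record. The SAP tests it only as within-group change at each visit and specifies no worst post-baseline grade, no share ever moderate or severe, and no between-arm comparison. The last of these falls short of Protocol 17.2.2 on its plain reading. SAP 5.6.1.2 says differences from the protocol are stated in the SAP, and none is stated here.

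Per-visit figures can understate the share ever affected by anything from nothing to about 4-fold in the four-visit case. The upper figure assumes one peak per subject, spread evenly over Days 7, 14, 28 and 35. The documents give no rate, duration or timing of reactions, so where the trial would fall in that range is unknown. It does not follow that the report would hide harm, only that the planned summaries are poorly suited to showing it. The primary efficacy analysis is unaffected.

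**What to change.** Add one table by treatment group to SAP 5.6.7.3, with:
- n (%) at each worst post-baseline grade, 0 to 4, for each component;
- n (%) with a worst grade of 3 or higher, and of 4, in any component, shown also as worsening from the Day 1 Pre-Dose score so that baseline skin findings are not counted as reactions;
- the maximum composite score;
- exact 95% CIs, and the difference of each active arm from placebo.

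Use all scheduled visits and any unscheduled visit at which LSR was recorded, and keep subjects in whatever their dose holiday or discontinuation status.

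The cost is SAP wording and one table; no new data are needed. Worst-score figures are higher than visit means in every arm, placebo included, so they must be read against placebo and not on their own. With 28 per arm the intervals will be wide, and the table is descriptive. The planned per-visit tables and figures should stay, because they show timing and recovery, which a worst-score table does not.

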5.6.7.7.5 QTcF interval (ms)

5.6.7.7.6 QTcB interval (ms)

- 5.6.7.8 The mean from Day 1 Pre-dose will serve as the ECG baseline to which all post dose ECG data will be compared. If the Day 1 value is missing, the Screening Visit value will be used as baseline.
- 5.6.7.9 For QT, QTcB and QTcF, absolute and relative frequency of patients with absolute result  $\geq 500$  ms at each visit will be displayed.
- 5.6.7.10 The changes from baseline in vital signs, ECG derived variables, clinical laboratory tests results will be analyzed by treatment group, using the Paired T-test if data is considered normally distributed or using the non-parametric Signed rank test (paired observations) if considered non-normal.
- 5.6.7.11 For QT, QTcB and QTcF (ECG data), absolute and relative frequency of increase above baseline divided into three categories  $< 30$  ms, 30-60 ms and  $> 60$  ms at each visit will be displayed.
- 5.6.7.12 Concomitant medication verbatim terms (as recorded on the CRFs) will be coded to Anatomical Therapeutic Chemical (ATC) Level 2 and 4 using the World Health Organization (WHO) dictionary.

	DOCUMENT NUMBER: 029-BST-PLN-001	PAGE: 35 of 45
TITLE: Statistical Analysis Plan for study: A Phase 2 Randomized, Double-Blind, Placebo-Controlled, Parallel-Cohort Study to Evaluate the Efficacy, Safety, Tolerability, and Pharmacokinetics of Once-Daily Application of Topical VDA-1102 Ointment for 28 Days in Subjects with Actinic Keratosis	EFFECTIVE DATE : 22/MAY/2017 REVISION NUMBER : 2.0	

## 5.6.8 PK Analysis

5.6.8.1 Non-compartmental PK will be calculated where applicable, if there are sufficiently high concentrations of VDA-1102 and/or its main metabolite for consistent calculations, using appropriate software. The PK sub-cohort including up to 18 subjects will be used.

5.6.8.2 The following PK parameters will be calculated:

5.6.8.2.1  $C_0$  – Pre-dose plasma concentration;

5.6.8.2.2  $C_{\max}$  - Maximum plasma concentration;

5.6.8.2.3  $T_{\max}$  - Time to reach the maximum plasma concentration;

5.6.8.2.4  $AUC_{\text{last}}$  - Area under the plasma concentration-time curve from time of administration up to the last time point with a measurable concentration post dosing, calculated by linear up-logarithmic down trapezoidal summation.

5.6.8.2.5  $AUC_{\infty}$  - Area under the plasma concentration-time curve extrapolated to infinity, calculated as:  $AUC_{\infty} = AUC_{\text{last}} + Clast/\lambda_z$ , where  $Clast$  is the last measurable concentration.

5.6.8.2.6  $\lambda_z$  - Elimination rate constant, determined by linear regression of the terminal points of the ln-linear plasma concentration-time curve;

5.6.8.2.7  $T_{1/2}$  - Terminal elimination half-life, defined as  $0.693/\lambda_z$ ;

5.6.8.3 Total AUC is calculated by summation of partial AUCs using the trapezoidal rule.

5.6.8.4 An individual segment ( $AUC_i$ ) is calculated using the following formulation:

$$AUC_1 = ( (C_0 + C_1) \times Time_{1-0} ) / 2$$

	DOCUMENT NUMBER: 029-BST-PLN-001	PAGE: 36 of 45
TITLE: Statistical Analysis Plan for study: A Phase 2 Randomized, Double-Blind, Placebo-Controlled, Parallel-Cohort Study to Evaluate the Efficacy, Safety, Tolerability, and Pharmacokinetics of Once-Daily Application of Topical VDA-1102 Ointment for 28 Days in Subjects with Actinic Keratosis	EFFECTIVE DATE : 22/MAY/2017 REVISION NUMBER : 2.0	

5.6.8.5 Where:

- 5.6.8.5.1  $C_0$  is the concentration measured on time 0
- 5.6.8.5.2  $C_1$  is the concentration measured on time point 1 (the next time point)
- 5.6.8.5.3  $Time_{1-0}$  is the time difference between time 1 and time 0.

5.6.8.6 The total AUC equals a summation of all partial AUC segments.

5.6.8.7 The calculated PK parameters as well as the raw data used for the calculations will be transferred to MediStat for generating a statistical report.

5.6.8.8 Medistat will further QA the data before generating the report. The QA will include checking for outlier measures and missing data.

5.6.8.9 MediStat will prepare a statistical report based on the raw data and the calculated PK parameters.

5.6.8.10 The data will be treatment blinded. Following data lock the treatment codes will be exposed and merged into the data and to be included in the statistical report

5.6.8.11 The report will include:

5.6.8.11.1 Summary tables of VDA-1102 and jasmonic acid plasma concentration by treatment and time point

5.6.8.11.2 Summary tables of PK parameters by treatment.

5.6.8.11.3 Individual listings of VDA-1102 and jasmonic acid plasma concentration

5.6.8.11.4 Individual listings of PK parameters

5.6.8.11.5 Graphical displays presenting mean concentration by time point

5.6.8.11.6 Individual figures presenting concentration by time point

	DOCUMENT NUMBER: 029-BST-PLN-001	PAGE: 37 of 45
TITLE: Statistical Analysis Plan for study: A Phase 2 Randomized, Double-Blind, Placebo-Controlled, Parallel-Cohort Study to Evaluate the Efficacy, Safety, Tolerability, and Pharmacokinetics of Once-Daily Application of Topical VDA-1102 Ointment for 28 Days in Subjects with Actinic Keratosis	EFFECTIVE DATE : 22/MAY/2017 REVISION NUMBER : 2.0	

5.6.8.12 Summary tables will be presented including sample size (N), mean, standard deviation, standard error, median, minimum and maximum values and 95% confidence intervals by treatment.

5.6.8.13 The data will be analysed using the SAS ® version 9.3 (SAS Institute, Cary North Carolina).

MediStat Statistics in Medicine	DOCUMENT NUMBER: 029-BST-PLN-001	PAGE: 38 of 45
TITLE: Statistical Analysis Plan for study:  A Phase 2 Randomized, Double-Blind, Placebo-Controlled, Parallel-Cohort Study to Evaluate the Efficacy, Safety, Tolerability, and Pharmacokinetics of Once-Daily Application of Topical VDA-1102 Ointment for 28 Days in Subjects with Actinic Keratosis	EFFECTIVE DATE : 22/MAY/2017 REVISION NUMBER : 2.0	

## 6. RELATED DOCUMENTS

### 6.1 Internal Documents

Not Applicable

### 6.2 External documents

6.2.1 VDA-CP-03 P2a 09June2016\_DL.pdf

6.2.2 VDA-CP-03 Listing appendix of 029-BST-SOP-002

6.2.3 VDA-CP-03 Tables appendix of 029-BST-SOP-002

MediStat Statistics in Medicine	DOCUMENT NUMBER: 029-BST-PLN-001	PAGE: 39 of 45
TITLE: Statistical Analysis Plan for study:  A Phase 2 Randomized, Double-Blind, Placebo-Controlled, Parallel-Cohort Study to Evaluate the Efficacy, Safety, Tolerability, and Pharmacokinetics of Once-Daily Application of Topical VDA-1102 Ointment for 28 Days in Subjects with Actinic Keratosis	EFFECTIVE DATE : 22/MAY/2017 REVISION NUMBER : 2.0	

## 7. RELATED FORMS

Not Applicable

MediStat Statistics in Medicine	DOCUMENT NUMBER: 029-BST-PLN-001	PAGE: 40 of 45
TITLE: Statistical Analysis Plan for study:  A Phase 2 Randomized, Double-Blind, Placebo-Controlled, Parallel-Cohort Study to Evaluate the Efficacy, Safety, Tolerability, and Pharmacokinetics of Once-Daily Application of Topical VDA-1102 Ointment for 28 Days in Subjects with Actinic Keratosis	EFFECTIVE DATE : 22/MAY/2017 REVISION NUMBER : 2.0	

## 8. REFERENCES

Not Applicable

MediStat Statistics in Medicine	DOCUMENT NUMBER: 029-BST-PLN-001	PAGE: 41 of 45
TITLE: Statistical Analysis Plan for study:  A Phase 2 Randomized, Double-Blind, Placebo-Controlled, Parallel-Cohort Study to Evaluate the Efficacy, Safety, Tolerability, and Pharmacokinetics of Once-Daily Application of Topical VDA-1102 Ointment for 28 Days in Subjects with Actinic Keratosis	EFFECTIVE DATE : 22/MAY/2017 REVISION NUMBER : 2.0	

